Effect of confounding: The overall rate ratio can be written as: $R = c \cdot R_v + (1-c)R_u$, where R_v is the rate ratio comparing vaccinated children in implementation areas and unvaccinated children in comparator areas, and R_u is the rate ratio comparing unvaccinated children in implementation and comparator areas, and R is the overall rate ratio that we observe directly. If there is no confounding (as if vaccination essentially assigned at random), $R_u = 1$ and $R = cR_v + 1 - c$. The observed R could then be compared with expected value if R_v was equal to the rate ratio in vaccinated children in the phase 3 trial for a given value of c . If there is confounding, $R_v = (F \times R_v^*)$, $R_u = (G \times R_u^*)$, where R_v^* is the true (unconfounded) rate ratio vaccinated:unvaccinated, $R_u^* = 1$ by definition, and F and G represent the confounding, i.e. F is the factor by which the rate in the RTS,S-vaccinated is increased relative to the unvaccinated comparator population, aside from any effect of the RTS,S vaccine, and G the

factor by which the rate in those that did not receive RTSS, is increased relative to the comparator population.

Confounding with respect to malaria outcomes: Preliminary estimates from the baseline surveys in each country, during which children 5-48 months were tested for malaria infection using an RDT and receipt of routine vaccinations was recorded, there was no evidence that coverage of basic vaccines was associated with malaria prevalence, suggesting confounding with respect to malaria outcomes may not be important.

Confounding with respect to meningitis: Apart of any effect of RTSS itself, the rate of meningitis is likely to be higher in the RTSS-unvaccinated and lower in the RTSS-vaccinated, because children who receive RTSS also more likely to have had pneumococcal and Hib vaccines, which protect against meningitis, than children who did not receive RTSS, unless high levels of coverage of pneumococcal and Hib vaccines have essentially eliminated vaccine serotypes from circulation. Conservatively, if say 90% of the population received anti-meningitis vaccines, and coverage of RTSS-1 is 80%, and 84% of those who received anti-meningitis vaccines also receive RTSS-1, then coverage of anti-meningitis vaccine among those who receive RTSS-1 is 95% and 70% in those who do not receive RTSS-1:

		RTSS-1		
		Y	N	Total
Anti-meningitis vaccine	Y	760	140	900
	N	40	60	100
Total:		800	200	1000

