Coverage of pneumo-2:		760/800=0.95	140/200=0.7	900/1000=0.9

If efficacy of anti-meningitis vaccine against meningitis of any cause is 70%, then the rate in RTSS recipients (before any RTSS effect) is reduced by a factor $0.95 \times (1 - 0.7) + (1 - 0.95) = 0.335$, compared to a factor of $0.9 \times (1 - 0.7) + 0.1 = 0.37$ in the unvaccinated comparator population, a rate ratio of $0.335 / 0.37 = 0.905$. Among those who do not receive RTSS-1, the corresponding factor is $0.7 \times (1 - 0.7) + 0.3 = 0.51$, compared to 0.37 in the comparator population, a rate ratio of $0.51 / 0.37 = 1.378$:

	RTSS-1	no RTSS-1
anti-meningitis vaccine coverage:	0.95	0.7
rate of meningitis reduced by factor:	$0.95 \times (1 - 0.7) + 0.05 = 0.335$	$0.7 \times (1 - 0.7) + 0.3 = 0.51$
Comparator population:		
anti-meningitis vaccine coverage:	0.9	
rate of meningitis reduced by factor:	$0.9 \times (1 - 0.7) + 0.1 = 0.37$	
rate ratio:	$0.335 / 0.37 = 0.905$	$0.51 / 0.37 = 1.378$

The observed rate ratio comparing implementation and comparator areas is:

$R=c.(F \times R_v^*)+(1-c).G$, with $F=0.905$, $G=1.378$ in this example. If the true (unconfounded) rate ratio was $R_v^*=10.5$ (as in the phase 3), and coverage of RTSS-1 was 80%, we would expect to see a rate ratio $R=0.8 \times 0.905 \times 10.5+(1-0.8) \times 1.378=7.878$ between implementation and comparator areas. To be able to rule out an association with meningitis of the magnitude seen in the phase 3 trial we would therefore want to be able to exclude rate ratios of about 7.9 or more. This compares with a value of $0.8 \times 10.5+0.2=8.6$ if there was no confounding.

Contamination:

Contamination could occur due to:

- a) Children in comparator clusters receive the malaria vaccine (either by attending a clinic in an implementation area instead of “their own” clinic, OR by moving address, after they have been vaccinated, from an implementation to a comparator cluster), so there is some benefit (or harm) in comparator areas, diluting our estimates of impact which compare implementing and comparator clusters;
- b) Children in intervention clusters receive their vaccinations from a clinic in a comparator area (by going to the “wrong” clinic, or by moving address after completing vaccination), so coverage of the vaccine in intervention areas, is lowered;
- c) Cases or deaths, who are assigned to the wrong cluster by mistake.

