Data will be reviewed by the DSMB at 6-monthly intervals. If there is evidence of increased incidence of safety outcomes in implementation clusters in vaccine-eligible age groups, vaccination status of cases in these groups would be examined, to determine if the proportion vaccinated is consistent with an excess given the level of vaccine coverage from administrative data; sensitivity analysis would be done to explore effects on results of uncertainties in age, missing data, and alternative case definitions; incidence of all cause admissions and admissions for conditions unrelated to the vaccine, would be compared between implementation and comparator areas to understand potential biases; and analysis will be done to determine if the results are similar in all three countries. If after completing these analyses, the data are consistent with an increased risk of adverse outcomes associated with RTS,S introduction, there will be an assessment of the magnitude of the excess risk in relation to evidence on potential benefits, to decide whether to recommend suspending or discontinuing vaccination.

Final analyses will be done when data up to month 46 are complete in all countries. Figure shows the accrual of person time, in the three countries combined, during the evaluation. During the latter half of the evaluation the total person time increases by a factor of more than 4.

9. Rebound effects

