For each main outcome, the proportion of cases/admissions who received 0,1,2 3 and 4 doses of RTS,S will be tabulated by cluster, eligibility group, and implementation/comparator area. This will indicate the degree of contamination (RTS,S recipients in comparator clusters), and whether children in group B in RTS,S clusters, may have received RTS,S. Among deaths which occurred in children of vaccine-eligible age in RTS,S/AS01 areas, the proportion who had received RTS,S/AS01 should be similar in boys and girls, if there is no differential effect of the vaccine on survival of boys and girls, since uptake of vaccination is generally very similar for boys and girls and this would be expected to hold also for RTS,S/AS01. Among cases of cerebral malaria, the proportion who received RTS,S/AS01 would be expected to be similar to the RTS,S/AS01 coverage in the general population of the same age, if RTS,S/AS01 has no effect on incidence of cerebral malaria. For meningitis, the comparison of vaccination status of cases with vaccine coverage in the population is complicated by the fact that receipt of RTS,S/AS01 is likely to be strongly associated with receipt of pentavalent and pneumococcal vaccine, which could mask an association with RTS,S/AS01.

Table 7: Dummy table for comparison of vaccination status of cases between areas

Outcome (4 tables: all deaths; all admissions; meningitis; severe malaria)	Vaccine	RTS,S Group A	RTS,S Group B	Comparator Group A	Comparator Group B
	RTS,S doses	% (n/N)			
	0				
	1				
	2				
	3				
	4				
	pentavalent doses				
	0				
	1				
	2				
	3				

16. EPI data

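### For meningitis, the SAP's follow-up check on a safety signal compares vaccinated cases with crude administrative coverage, a benchmark that its own confounding assumptions make about 7 to 8 points too high

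*SAP*

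**What the plan says.** The step stands near the end of SAP section 8, in the paragraph on six-monthly DSMB review. When a safety outcome appears raised in vaccine-eligible children in implementation clusters, the vaccination status of those cases is examined "to determine if the proportion vaccinated is consistent with an excess given the level of vaccine coverage from administrative data". Three other analyses sit beside it: sensitivity analyses (age, missing data, case definitions), a comparison of all-cause and unrelated admissions between areas, and a check that the three countries agree. The weighing of risk against benefit, and any advice to suspend or discontinue, comes next: "If after completing these analyses, the data are consistent with an increased risk of adverse outcomes associated with RTS,S introduction". The paragraph covers all safety outcomes and does not adjust the coverage benchmark for any of them.

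Earlier in section 8, under confounding with respect to meningitis, the SAP says that, apart from any RTS,S effect, "the rate of meningitis is likely to be higher in the RTSS-unvaccinated and lower in the RTSS-vaccinated". The reason given is that RTS,S uptake goes with pneumococcal and Hib vaccination. Its example has "coverage of anti-meningitis vaccine among those who receive RTSS-1 is 95% and 70% in those who do not receive RTSS-1" and gives factors relative to the comparator population, "with $F=0.905$, $G=1.378$ in this example".

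SAP section 15 (Comparison between groups) returns to the comparison of cases with population coverage. It says that for meningitis the association of RTS,S with pentavalent and pneumococcal vaccine is a complication "which could mask an association with RTS,S/AS01". It gives no corrected benchmark.

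**The concern.** Comparing the vaccinated share of cases with population coverage is a screening-method argument. Coverage is the right reference only if vaccinated and unvaccinated children would have the same rate without the vaccine. For meningitis the SAP assumes that they would not. It carries that assumption into its power targets (the 7.9 of the worked example and the confounding column of Table 5), but not into the step that helps the DSMB decide whether an apparent increase is real. A vaccinated share equal to coverage would look like no excess when, on the SAP's own assumptions, it would point to some increase. At stake is how much weight a meningitis signal from the area comparison keeps when this check is read beside it.

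**Working it through.** **Inputs.**
- Worked example (SAP 8, confounding with respect to meningitis): RTS,S dose 1 coverage c = 0.80; anti-meningitis vaccine coverage 90% overall, 95% in recipients and 70% in non-recipients; efficacy 70%.
- Table 5, footnotes 2 and 4: c = 0.74; anti-meningitis coverage 90%; efficacy 50%; all RTS,S recipients covered.
- Phase 3 meningitis rate ratio: 10.5 (Table 5).

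**Reproducing the SAP's figures.** F = (0.95×0.3 + 0.05)/(0.9×0.3 + 0.1) = 0.335/0.37 = 0.905. G = (0.70×0.3 + 0.30)/0.37 = 0.51/0.37 = 1.378. The area-level ratio is R = c·F·Rv + (1−c)·G, where Rv is the true ratio in vaccinated children. For Rv = 10.5, R = 0.8×0.905×10.5 + 0.2×1.378 = 7.878, as the SAP states. Without confounding it is 0.8×10.5 + 0.2 = 8.6, also as stated.

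**Vaccinated share of cases.** From the same model, share = c·F·Rv / [c·F·Rv + (1−c)·G]. With no effect (Rv = 1) the share is c·F / [c·F + (1−c)·G].
- Worked example: 0.724/(0.724 + 0.2756) = 72.4%, against coverage of 80%.
- Table 5 inputs: F = 0.50/0.55 = 0.909. Anti-meningitis coverage in non-recipients is (0.90 − 0.74)/0.26 = 0.615, so G = (1 − 0.5×0.615)/0.55 = 0.692/0.55 = 1.259. The null share is 0.6727/(0.6727 + 0.3273) = 67.3%, against 74%.

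The gap is 7.6 points in the first case and 6.7 in the second.

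**Effect on the implied ratio.** Taking coverage as the null, the implied ratio is [share/(1−share)]×[(1−c)/c] = Rv·F/G. F/G is 0.66 in the worked example and 0.72 with Table 5 inputs.

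| True Rv | Share, c = 80% | Implied Rv | Share, c = 74% | Implied Rv |
|---|---|---|---|---|
| 1 | 72.4% | 0.66 | 67.3% | 0.72 |
| 2 | 84.0% | 1.31 | 80.4% | 1.44 |
| 3 | 88.7% | 1.97 | 86.1% | 2.17 |
| 10.5 | 96.5% | 6.90 | 95.6% | 7.58 |

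The share equals coverage when Rv = G/F, which is 1.52 (area-level R = 1.38) or 1.38 (R = 1.26).

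**Chance, with few cases.** The documents give no count of eligible implementation-area meningitis cases, so 20, 30 and 60 are assumed here. In the worked example with true Rv = 2, the observed share is at or below 80% with probability 40%, 35% and 24%. With Rv = 3 it is 18%, about 11% and 3%. With Rv = 10.5 it is under 1% throughout.

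**Sensitivity.** Assume all RTS,S recipients have the anti-meningitis vaccines, RTS,S coverage is 69–80%, anti-meningitis coverage 85–93% and efficacy 30–70% (values beyond the SAP's are assumptions). The null share then falls 2 to 21 points below coverage, and the break-even Rv runs from 1.10 to 2.75.

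**The case against.** A reader might infer that this check can dismiss a real increase and so block a recommendation to suspend. The documents do not support that.
- The check starts only after the area comparison has shown evidence of increased incidence. It is one of four analyses, and none has a threshold or a veto.
- The effects fully hidden on average (area-level 1.26 to 1.38) would rarely trigger it. The evaluation was designed for a 2.6-fold increase over 46 months (SAP 2) and expects power for a 5-fold increase at month 24 (SAP 8). Even at month 45 the smallest ratio excludable with 80% power is 2.9 (SAP Annex 4, A4.2).
- At area-level 2.6 in the worked example, Rv = (2.6 − 0.2756)/0.724 = 3.21 and the expected share is 2.324/2.6 = 89%, still above 80%.

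All of that stands, and it limits the point to weakening a signal.

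The step can also be read as asking whether the share fits the observed excess, with expectation 1 − (1−c)/R. That expectation is still too high under the SAP's confounding, though the gap is small: 88.4% against 84.0% at R = 1.72, and 92.3% against 89.4% at R = 2.6. The latter is about 0.6 standard errors with 30 cases.

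The SAP also has population A4 (penta3 recipients, section 7), and Table 7 tabulates pentavalent doses of cases. A4 adjusts the rate comparison between areas, and Table 7 supplies data. Neither changes the benchmark in the section 8 step.

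Finally, F and G come from a hypothetical example, and the SAP notes that the confounding may not arise if high coverage has all but eliminated vaccine serotypes. So 72% is illustrative, not the correct value, which is why the benchmark should be a range.

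**Conclusion.** The point holds for meningitis. On the SAP's own assumptions, crude administrative coverage is about 7 to 8 points too high as the reference for the vaccinated share of cases, and it understates the implied rate ratio by a factor of about 0.66 to 0.72. The check can therefore weaken or understate a real signal, most plausibly a 2- to 3-fold effect in vaccinated children with few cases. It would not hide an effect of phase 3 size. Section 15 recognises the masking, so the gap is that the section 8 step neither refers to it nor corrects for it. The size rests on the SAP's illustrative F and G and shrinks to nothing if F = G = 1. The point does not extend to the malaria outcomes, for which the SAP expects no important confounding.

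**What to change.** This is a cheap improvement. In the DSMB review paragraph of SAP section 8, for meningitis only:
1. Compare the vaccinated share of cases with c·F/(c·F + (1−c)·G) over a stated range of F and G that includes F = G = 1, using administrative coverage for c at the six-monthly reviews.
2. When survey data are available, add a comparison within penta3 strata: RTS,S status of cases against survey RTS,S coverage in children of the same penta3 status, country and age band. Use PCV strata only if PCV is actually entered. Protocol Annex 12 asks for all vaccines in meningitis cases, but its notes limit entry to the third pentavalent dose and RTS,S doses.
3. State that a share equal to crude coverage is not evidence against a meningitis signal, and cross-refer to section 15.

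The cost is SAP wording and a short calculation on data already planned. The drawbacks are fewer cases per stratum, reliance on cases with known vaccine status, and a benchmark given as a range. Survey coverage exists only around months 18 and 30, and the first of these surveys covers ages 12–23 months only, so the stratified comparison cannot replace step 1 at every review.

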### 7.1 Efficacy of RTS,S/AS01

RTS,S/AS01, the world's first malaria vaccine, was evaluated in a phase 3 trial in 15,459 infants (6-12 weeks old at the time of dose 1) and young children (5-17 months old at the time of dose 1) in 7 sub-Saharan African countries. Three doses of RTS,S/AS01 generated protection against clinical malaria which, though moderate compared with the efficacy achieved by vaccines against common viral diseases, is substantial in the context of malaria where there is a very high burden of disease and available interventions cannot offer high levels of protection (table 1). In the 12 months following completion of the primary vaccination course in children aged 5-17 months at the time of dose 1, the incidence of clinical malaria was reduced by 51% and the incidence of severe malaria was reduced by 44.5%. Protection appeared to wane over time: by 18 months after the primary vaccination course, efficacy was 46% against clinical malaria and 38% against severe malaria. Efficacy against clinical malaria of 3 doses alone declined in the successive 6-months periods from 68% in the first 6-month interval to 39% and 28% in the successive 6-month intervals. A fourth dose, given 18 months after dose 3, increased efficacy to 39% against clinical and 31.5% against severe malaria over the whole of the study (a median of 48 months follow-up) whereas, among the children randomised to receive only three doses of RTS,S/AS01, efficacy against clinical malaria fell to 26% and against severe malaria to -2.2%. The 4th dose of RTS,S/AS01 therefore appears to be needed to maintain efficacy against severe malaria.

Over the whole (median 4-year) follow-up of children in the phase 3 trial, vaccine efficacy was also confirmed against malaria hospitalization (37%, ATP, 95%CI 27-48.5), all-cause hospitalization (15%, ATP, 95%CI 6-25) and severe anaemia (62%, ATP, 95%CI 26.5-81). These benefits were demonstrated in the presence of high ITN coverage and where the identification and treatment of clinical and severe malaria episodes, as well as other medical care, was optimized. The enhanced access to good quality curative services likely limited disease progression and precluded the measurement of vaccine impact on mortality. However, modelling suggests a substantial potential survival impact of RTS,S/AS01 outside trial settings (1 life saved per 200 fully vaccinated children in moderate to high transmission settings).

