In the phase 3 trial of the vaccine conducted from 2009 to 2014 [2], in children who received four vaccine doses (three primary doses and a fourth dose 18 months later), the incidence of uncomplicated malaria and of severe malaria were reduced by 39% and 32% respectively over 4 years of follow-up. For every 1000 children vaccinated with 4 doses, a total of 1774 cases of malaria and 40 hospital admissions due to malaria were averted over about 4 years¹. A total of 19 cases of severe malaria were averted, cases which, without the enhanced access to care provided in the context of the trial, might have led to death. The vaccine therefore could have a substantial public health impact.

The current vaccination schedules include three primary doses to be administered before 9 months of age and a fourth dose at about 2 years of age. This involves three to four additional vaccination visits than are currently recommended in this age range. The MVPE seeks to determine the impact realised in practice when the vaccine is introduced in areas of high to moderate malaria incidence in three countries with year-round malaria transmission. The programme will evaluate the safety of RTS,S/AS01 in routine use, the feasibility of administering four doses of the vaccine, and the impact of the vaccine at population level, using a cluster-randomized design. The vaccine is being introduced sub-nationally in pilot areas in each of the three countries, by the EPI programme. Within the pilot area in each country, districts (in Ghana), subcounties (in Kenya), and clusters of equivalent population (in Malawi), have been randomized to either introduce the vaccine in 2019 (implementation clusters), or to delay introduction until the initial introduction has been evaluated (comparison clusters). Thus, the evaluation will use a cluster-randomized design. Community reporters will document all deaths occurring in children under 5 years of age in the implementation and comparison clusters. Hospital surveillance is being established in sentinel hospitals in a subset of clusters to monitor the incidence of admission with malaria and other conditions. Vaccine administration will be delivered through, and monitored by, the Expanded Programme for Immunization (EPI) in each country and uptake of RTS,S/AS01 will also be measured independently through cluster-sample household surveys.

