The MVPE will determine whether the introduction of RTS,S/AS01 leads to a reduction in child deaths, and a reduction in the incidence of hospital admission with severe malaria, over the 4 years of the implementation programme (MVIP, Malaria Vaccine Implementation Programme). The MVPE also addresses three safety signals that were observed in the phase 3 trial but whose significance was unclear: an unexplained excess of meningitis cases in RTS,S/AS01 recipients, an excess in cerebral malaria cases among RTS,S/AS01 recipients who developed severe malaria and, among the relatively small number of deaths that occurred in the trial, an excess of deaths among girls who received RTS,S/AS01 compared to girls who did not receive RTS,S/AS01. The data to be collected

¹ In the phase 3 trial, for every 1000 children vaccinated with 4 doses, a total of 1774 (95% CI 1387–2186) cases of malaria, 40 (95% CI 19–64) hospital admissions due to malaria, and 19 (95% CI 4 to 35) cases of severe malaria, were averted over about 4 years.

over 4 years will inform a policy decision about wider use of RTS,S/AS01 as a means to reduce malaria morbidity and mortality, when provided in addition to existing malaria control measures. It is anticipated that sufficient data to assess the safety signals are likely to be available after the first 2 years of the evaluation. At that time, all available data would be reviewed, including outcomes related to safety of the vaccine in routine use (meningitis, cerebral malaria, mortality by gender, AEFI), the impact on severe malaria and all-cause mortality, coverage of the first 3 doses, preliminary data on administration of the 4th dose, and cost-effectiveness assessment. A recommendation about wider use of the vaccine might therefore be made before final impact data are available, recognizing that the impact in any setting will depend on coverage and timeliness of vaccination and the malaria burden, which may differ from those in the MVIP [3].

2. Design of the evaluation

A total of 158 clusters, 66 in Ghana, 46 in Malawi and 46 in western Kenya, each cluster with a total population of about 100,000 on average, were randomized to either introduce RTS,S/AS01 vaccine in 2019 or to delay introduction until a decision is reached about safety and effectiveness.

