Mortality (all causes)	Death due to any cause
Malaria-associated mortality in hospital	Death in hospital in an individual who has confirmed malaria
Severe malaria	P.falciparum infection detected by RDT (antigenaemia detected by RDT or in the absence of RDT result, parasitaemia by microscopy at any density) AND one or more of the following: a) impaired consciousness (Glasgow coma score <11, Blantyre coma score <3, or assessed as P or U on the AVPU score and not positive for probable or confirmed meningitis; b) multiple of atypical convulsions (more than two episodes within 24 hours or prolonged (>15minutes), or focal) and not positive for probable or confirmed meningitis; c) respiratory distress (manifested as chest indrawing or deep breathing); d) severe malaria anaemia (haemoglobin concentration <5g/dL or haematocrit <15%).
Cerebral malaria (broader)	P.falciparum infection (by RDT or microscopy, as above) with impaired consciousness (Glasgow coma score <11 or Blantyre coma score <3 or assessed as P or U on AVPU score), excluding cases with CSF findings consistent with probable meningitis.
Cerebral malaria (stricter, LP required)	P.falciparum infection (by RDT or microscopy, as above) with impaired consciousness (Glasgow coma score <11 or Blantyre coma score <3 or assessed as P or U on AVPU score) AND CSF findings not consistent with probable meningitis (this strict cerebral malaria diagnosis cannot be made without an LP).
Severe malaria (stricter)	P.falciparum infection (as above) AND one or more of the following: a) impaired consciousness (Glasgow coma score <11, Blantyre coma score <3, or assessed as P or U on the AVPU score and negative for meningitis (LP performed); b) multiple of atypical convulsions (more than two episodes within 24 hours or prolonged (>15minutes), or focal) and negative for meningitis (LP performed); c) respiratory distress (manifested as chest indrawing or deep breathing); d) severe malaria anaemia (haemoglobin concentration <5g/dL or haematocrit <15%).
Probable meningitis	Children will be considered to have “probable meningitis” if in a suspected case*, the macroscopic aspect of the CSF is turbid, cloudy or purulent; or the CSF leukocyte count is >10 cells/mm ³ .
Confirmed meningitis	Any suspected or probable case, laboratory confirmed by culture or PCR to be of bacterial, viral or other aetiology in the CSF.

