- % children who received RTS,S4 who had previously received less than 3 doses of RTS,S.

18. Other interventions that might affect MVPE outcomes

A diary of other interventions (e.g. LLIN distribution, IRS campaigns, azithromycin MDA, expansion of community case management, creation of new health facilities) maintained for each cluster would allow reporting of contextual information about the possible influence of other interventions taking place in study clusters during the MVIP. These are being recorded by the evaluation partners and reported to WHO as part of quarterly technical reports. Likewise, the PATH and WHO MVIP team members in each pilot country records similar events that can affect EPI delivery of the RTS,S vaccine.

19. Calculation of rate ratios and rate differences

Incidence of the primary safety outcomes (probable meningitis, confirmed meningitis, cerebral malaria) and impact outcomes (deaths, deaths excluding injuries, and severe malaria) will be compared between comparator and RTS,S areas, in each country and for the three countries combined. For mortality, the evaluation is powered to estimate effects within each country by the end of the 46 months. For meningitis, primary analysis will be pooled across the three countries.

Rate ratios and rate differences, with 95% and 99% confidence intervals, will be calculated as in the table below. Secondary safety and impact outcomes listed in Table 5 will be analysed in the same way.

Table 8: Dummy table for effect measures for safety and impact outcomes

Outcome	Analysis populations* primary (secondary)	Comparator N/PYAR rate	RTS,S N/PYAR rate	Rate ratio (95%CI)	Rate difference (95%CI)
Safety:					
Probable meningitis	A1 (A4)				
Confirmed meningitis	A1 (A4)				
Cerebral malaria	A1 (A4)				
Impact:					
Deaths	A2 (A4)				
Deaths (excl. injury)	A2 (A4)				
Severe malaria	A2 (A4)				

*A1: eligible for RTS,S; A2: eligible for 3 doses of RTS,S; A4: received 3 doses of pentavalent vaccine

(Note: For severe malaria, if a reduction in the number of admissions for all-cause febrile illness is observed that is commensurate with the reduction in severe malaria, this would give reassurance that the reduction in severe malaria was not caused simply by a reduction in the prevalence of parasitaemia without prevention of severe illness.)

Subgroup analyses

Gender

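### The SAP's check that a fall in severe malaria is real also counts non-severe malaria, so it discriminates poorly if only milder malaria is prevented

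*SAP*

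**What the plan says.** Hospital admission with severe malaria is a primary impact outcome, analysed in population A2. SAP Table 3 requires one or more severity signs (impaired consciousness, multiple or atypical convulsions, respiratory distress, severe anaemia) plus evidence of infection, defined as "antigenaemia detected by RDT or in the absence of RDT result, parasitaemia by microscopy at any density". Fever is not required. A child who is severely ill from another cause and carries parasites incidentally can therefore qualify.

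The note under SAP Table 8 recognises this. It looks for reassurance that a reduction in severe malaria "was not caused simply by a reduction in the prevalence of parasitaemia without prevention of severe illness", and it would take that reassurance "if a reduction in the number of admissions for all-cause febrile illness is observed that is commensurate with the reduction in severe malaria". The comparison is in numbers of admissions. No tolerance is given for what counts as commensurate, febrile admission is not an outcome in Table 3, and non-severe malaria is not removed from the count.

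SAP section 1 gives the phase 3 results per 1000 children vaccinated with four doses: "a total of 1774 cases of malaria and 40 hospital admissions due to malaria were averted over about 4 years", and "A total of 19 cases of severe malaria were averted". Its footnote gives the intervals: "40 (95% CI 19–64) hospital admissions due to malaria, and 19 (95% CI 4 to 35) cases of severe malaria".

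**The concern.** The note asks whether severe illness was prevented or whether vaccinated children merely carried fewer parasites when severely ill from something else. Its yardstick also moves with non-severe malaria. If the vaccine prevents milder malaria admissions, febrile admissions fall whatever happens to severe illness, and that fall could be read as confirming the severe-malaria result.

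The mixed pattern is not fanciful. Protocol section 7.1 reports that three-dose recipients had 26% efficacy against clinical malaria and -2.2% against severe malaria over the whole trial, and SAP section 9 discusses that rebound. What is at stake is the interpretation of a primary outcome. The rate ratio and its interval are unaffected.

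**Working it through.** **Plan's own figures.** The note contains no number to reproduce. The nearest is the severe-malaria row of SAP Table 5. With coverage 0.74, contamination 0.04 and a trial rate ratio of 0.66:

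- after coverage: 0.74 × 0.66 + 0.26 = 0.748 (stated 0.75);
- after contamination: 0.748 / (0.04 × 0.66 + 0.96) = 0.759 (stated 0.76).

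The 19 per 1000 can only be approximated from protocol Table 1: (157/7664.8 − 101/7459.6) × (7459.6/2276) × 1000 = 22.8. This lies inside the stated interval of 4 to 35; the population or method may differ.

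**The check at point estimates (per 1000 vaccinated children).** Assume severe cases are a subset of malaria admissions. Non-severe admissions averted = 40 − 19 = 21. Let f be the share of the 19 apparently averted severe cases that were only relabelled as parasite-negative. The fall in febrile admissions is then 21 + (1 − f) × 19, treating all these admissions as febrile.

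| f | Febrile fall | Ratio to 19 |
|---|---|---|
| 0 (all real) | 40 | 2.11 |
| 0.5 | 30.5 | 1.61 |
| 1 (none real) | 21 | 1.11 |

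Every row meets the benchmark. Coverage scales both falls alike and leaves the ratios unchanged.

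**Uncertainty.** Standard errors from the stated intervals are (64 − 19)/3.92 = 11.48 for the 40 and (35 − 4)/3.92 = 7.91 for the 19. Taking the severe and non-severe falls as independent, the standard error of the 21 is √(11.48² − 7.91²) = 8.32, giving an approximate 95% interval of 5 to 37. For the non-severe fall to equal or exceed the severe fall, z = (21 − 19)/√(8.32² + 7.91²) = 0.174, a probability of about 57%. The probability of reaching 75% of the severe fall is about 75%, and of reaching 50%, about 89%.

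**If part of the 21 is also incidental.** With share g incidental, 21 × (1 − g) remains: 18.9 at g = 0.1, 15.75 at 0.25, 10.5 at 0.5 and 0 at 1. Strict equality with 19 is lost once g exceeds 1 − 19/21, about 10%.

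**Sampling error in the evaluation.** These simulations assume 74% coverage, 4,000 severe cases (Table 5), a design effect of 1 to 2, and 160 to 267 febrile admissions per 1000. The last range is 40/0.25 and 40/0.15, with all-cause admissions standing in for febrile ones. The proportions of runs in which the febrile fall equals or exceeds the severe-malaria fall are:

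- severe and non-severe prevention both real: about 92–100%;
- severe fall all artefact, non-severe fall real: 55–60%;
- severe fall all artefact, half to three-quarters of the non-severe fall real: 14–41%;
- both falls artefact: about 2–12%.

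**Reading commensurate as the same percentage.** Protocol section 7.1 gives four-dose efficacy of 31.5% against severe malaria and, for admissions, "malaria hospitalization (37%, ATP, 95%CI 27-48.5), all-cause hospitalization (15%, ATP, 95%CI 6-25". A same-percentage test would tend to fail even when prevention is real (15% against 31.5%).

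**What would separate the cases.** Count admissions with the severity signs regardless of malaria test. The expected fall is about 19 if prevention is real and about 0 if cases are only relabelled.

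**The case against.** The strongest reply is that the arithmetic treats the two kinds of malaria admission asymmetrically. A malaria admission in Table 3 needs only a positive test and no severity sign, so it is at least as open to incidental infection as severe malaria. If incidental infection drives both falls, febrile admissions do not fall and the check works, as the 2–12% figure shows. That stands, and it confines the weakness to the mixed case: severe illness not prevented, milder malaria prevented.

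Second, 21 against 19 is close, imprecise and dependent on the subset assumption. It comes from a trial with enhanced access to care, and the severe share in sentinel hospitals under the any-density definition is not given. That also stands, so the match is possible rather than assured.

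Third, the note is a parenthetical remark without a decision rule, and other evidence is planned: non-malaria admissions (which relabelling would tend to raise), all-cause admissions, severe malaria anaemia, transfusion and mortality. SAP section 9 looks for mortality findings consistent with a fall in severe malaria. A reader might infer that the note is the only safeguard, or that an artefact would be reported as confirmed; the documents support neither. The SAP does not, however, tie these outcomes to this question. The stricter severe-malaria definition does not settle it either, because it adds a lumbar-puncture requirement to the neurological criteria only.

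**Conclusion.** The concern holds in a limited form. On the SAP's phase 3 point estimates, the febrile fall could roughly match the severe-malaria fall (21 against 19 per 1000) with no severe illness prevented. The check therefore discriminates poorly in that mixed case. This rests on severe cases being a subset of malaria admissions, on the non-severe fall being real, and on the trial's severe to non-severe ratio carrying over.

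A reader might go further and infer that the check cannot tell real prevention from fewer incidental infections at all. The documents do not support that: it would expose the case where no febrile illness is prevented, and its pass rate is still higher when prevention is real (92–100%) than in the mixed case (55–60% or less). This is a worthwhile, inexpensive sharpening of a supportive check, not a fault in the primary analysis.

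**What to change.** Replace or supplement the note with a pre-specified supportive analysis in A2:

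- Define admissions meeting the Table 3 severity criteria for severe malaria (impaired consciousness, multiple or atypical convulsions, respiratory distress, severe anaemia) regardless of malaria test result. Keep the same thresholds and meningitis exclusions, so that the two outcomes differ only in the test.
- Estimate its rate ratio and rate difference with the section 20 estimator, and set the rate difference beside that for severe malaria, with confidence intervals.
- State the reading in advance: a similar fall supports real prevention; a fall near zero points to relabelling. Because rate differences add, the gap between the two is the change in severe-sign admissions without a positive test, which can carry its own interval.

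The cost is SAP wording and one more run of existing code. The downside is lower relative precision, because severe illness from other causes enters the count, so a wide interval should be reported as inconclusive.

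One point needs confirming first. Protocol section 10.3.3 and the Annex 12 form collect the severity signs, malaria test and haemoglobin for programme-area admissions generally, whereas SAP section 2 mentions clinical and laboratory details for suspected meningitis and severe malaria. If signs were missing for test-negative children, the new outcome would collapse towards severe malaria itself and the comparison would lose its value.
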